6 STUDY PROCEDURES

Subjects will be evaluated for study eligibility at a screening visit up to 30 days prior to enrollment on study. All laboratory tests done to confirm eligibility must be performed within 14 days unless otherwise noted prior to enrollment. Radiologic disease evaluations must be done within 30 days of enrollment. Subjects will be seen by medical providers for prior history, physical exam, and required assessments as noted below to monitor for toxicities and assess disease status. Any results falling outside of the reference ranges may be repeated at the investigator's discretion. All on-study visit procedures are allowed a window of ± 7 days unless otherwise noted. Treatment or visit delays for public holidays or weather conditions do not constitute a protocol violation but should be noted in the source documents.

6.1 Screening Assessments

Eligibility/screening studies and procedures to be performed at the screening visit (up to 30 days prior to enrollment with the exception of those noted # below).

- Informed Consent: A written, signed informed consent form (ICF)/a Health Insurance Portability and Accountability Act (HIPAA) authorization must be obtained before any study-specific assessments are initiated. A signed copy will be given to the subject and a copy will be filed in the medical record. The original will be kept on file with the study records.
- Documentation of validated laboratory result demonstrating a germline or somatic Ras/MAPK-pathway alteration.
- Medical history, physical examination (PE) including skin examination (Screening photograph(s) of cutaneous lesions, lymphedema, or other), medications, and medical records review including history of prior treatments and any residual toxicity relating to prior treatment.
- Height and Weight
- Vital Signs: temperature, pulse, blood pressure, respiratory rate, oxygen saturation by pulse oximeter
- Performance Status: Karnofsky/Lansky Performance Score.
- Laboratory Studies: as outlined in Table 6-1: Protocol-required Safety Laboratory Assessments

Table 6-1: Protocol-required Safety Laboratory Assessments

Laboratory Assessments	Parameters
Comprehensive Metabolic Panel	
 • Sodium • Potassium • Chloride • Carbon Dioxide • Urea Nitrogen • Creatine • Fasting Glucose • Calcium • Total Bilirubin • Total Protein • Albumin • Alkaline Phosphatase • Alanine Aminotransferase • Aspartate Aminotransferase
CBC with Differential	
 • Absolute Neutrophils • Absolute Lymphocytes • Absolute Monocytes • Absolute Eosinophils • Absolute Basophils • Absolute Immature Granulocyte • Nucleated RBC Automated • Platelet count • MPV • Neutrophils % • Lymphocytes % • Monocytes % • Eosinophils % • Basophils % • Immature Granulocyte % • Absolute Neutrophils • Absolute Lymphocytes • Absolute Monocytes • Absolute Eosinophils • Absolute Basophils • Absolute Immature Granulocyte • Nucleated RBC Automated
Coagulation	
 • Fibrinogen • D Dimer • PT/INR • PTT Profile
Additional Lab Studies	
 • CK • Lipase • Phosphorous • Magnesium
Pregnancy testing ¹	
 • Serum or urine pregnancy testing (within 7 days of starting study medication)
WBC= white blood cell; RBC= red blood cell; HGB= hemoglobin; HCT= hematocrit; MCV= mean	

corpuscular volume; MCH= mean corpuscular hemoglobin; MCHC= mean corpuscular hemoglobin concentration; RDW= red cell distribution; MPV= mean platelet volume; PT/INR = prothrombin time/international normalized ratio; PTT= partial thromboplastin time; CK=creatinine kinase

¹ Standard pregnancy testing for all people who can get pregnant of childbearing age

- Optional Biologic Studies
 - Biomarker
 - cfDNA
- Cardiac Assessment:
 - Echocardiogram
 - An age-appropriate transthoracic echocardiogram is recommended with interpretation by a pediatric or adult cardiologist. Documentation of left ventricular shortening fraction and left ventricular ejection fraction is required. Multigated acquisition scan (MUGA) may be substituted for echocardiogram at the discretion of the investigator with a documentation of the left ventricular ejection fraction. It will be completed at screening, at the end of cycles 1, 2, and 3, and after every 3 cycles until the end of the study.
 - ECG
 - An age-appropriate ECG is recommended with interpretation by a pediatric or adult cardiologist. Documentation of the corrected QTC interval is required. To be performed as part of screening, at the end of cycles 1, 2, and 3, and after every 3 cycles until the end of the study (not triplicate). To be repeated at investigator discretion only if clinically indicated.
- Ophthalmologic exam (Within 12 weeks of enrollment on trial): an age-appropriate ophthalmologic examination that avoids any sedation should be performed by an ophthalmologist at screening. This includes a Snellen examination (if age appropriate as determined by the ophthalmologist). The examination must include a funduscopy evaluation to rule out retinal vein occlusion (RVO) and retinal pigment epithelial detachment (RPED), can be dilated or non-dilated at discretion of ophthalmologist and can be accomplished using imaging with a non-mydriatic fundus camera.
- Individualized Response Criteria
 - Radiologic assessment (within 4 weeks of enrollment)
 - Radiologic assessment/imaging modality of choice based on underlying vascular anomaly (MRI, MRL, US, X-rays, CT scan)
 - Patient Reported Outcome (PRO) Measurement
 - PROMIS measures are not applicable or validated for subjects younger than 1 year of age. If infants younger than 1 year of age are enrolled in this study, they will not have PROs, and their response criteria will be determined by radiologic response and CBA.

Construct	Adult Subject	Parent Proxy	Parent Proxy 5-	Pediatric Subject 8-17
-----------	---------------	--------------	-----------------	------------------------

	18+ y/o	1-5 y/o	17 y/o	y/o
Primary Outcome for Individualized Response				
Global Health – Physical Health Subscale	PROMIS Scale v1.2 - Global Health	PROMIS Early Childhood Parent-Report Scale v1.0 - Global Health 8a	PROMIS Parent Proxy Scale v1.0 - Global Health 7+2	PROMIS Pediatric Scale v1.0 - Global Health 7+2
Secondary Outcome for Individualized Response				
Pain Interference	PROMIS Short Form v1.1 - Pain Interference 4a	N/A	PROMIS Parent Proxy SF GenPop v3.0 - Pain Interference 8a	PROMIS Pediatric SF GenPop v3.0 - Pain Interference 8a
Exploratory Outcomes				
Fatigue	PROMIS Short Form v1.0 - Fatigue 4a	N/A	PROMIS Parent Proxy SF GenPop v3.0 - Fatigue 10a	PROMIS Pediatric SF GenPop v3.0 - Fatigue 10a
Anxiety	PROMIS Short Form v1.0 - Anxiety 4a	PROMIS Early Childhood Parent-Report Short Form v1.0 - Anxiety 4a	PROMIS Parent Proxy SF GenPop v3.0 - Anxiety 8a	PROMIS Pediatric SF GenPop v3.0 - Anxiety 8a
Depression	PROMIS Short Form v1.0 - Depression 4a	PROMIS Early Childhood Parent-Report Short Form v1.0 - Depressive Symptoms 4a	PROMIS Parent Proxy SF GenPop v3.0 - Depressive Symptoms 6a	PROMIS Pediatric SF GenPop v3.0 - Depressive Symptoms 8a

○ Clinical Benefit Assessments (CBA)

At the screening visit, the site PI and treatment team with parental/patient input will determine the CBA or CBAs to be followed for that subject and will document during that study visit. If the site PI has any questions, they will be discussed with the Chair and Co-chair of the protocol.

Some suggestions for CBA: See [Appendix X](#).

Examples of testing or assessments that can be followed to complete this grading scale include:

- Pulmonary function testing
- Lymphedema staging
- Laboratory parameters
- Bleeding assessment
- PLE grading
- Effusion assessment
- Infection rates
- Seizure grading
- Photography
- Videos
- Patient narratives

6.2 Study Treatment Phase

Subjects must meet all eligibility criteria by Day 1 to continue into the study treatment phase. The study treatment phase begins with Cycle 1, day 1 and continues through 28-day cycles. Please refer to [Table 8-1 Schedule of Assessments](#) for required assessments.

6.2.1 Treatment Compliance and Adherence

Subjects will document medication adherence in a medication diary, [Appendix III](#) or [Appendix IV](#). The diary will be provided to the Investigator or designee at each visit, and the subject will then receive a new diary. Remaining medication volume or tablets will be reviewed at each study visit to assess adherence. At the dispensing visit, subjects will be asked to bring all remaining study drug supplies to their onsite visit to assess adherence to treatment.

6.3 Extension Phase of the Study

Subjects in the absence of toxicity and with clinical benefit may continue into the extension period for up to 12 additional cycles (36 total cycles, including the treatment phase). This will be at the discretion of the treating physician and subject/subject's family. A subject may receive extension therapy for a total duration of 36 cycles (including the first 24 cycles of study treatment).

6.4 Follow-up Phase

All subjects, including those who discontinue protocol therapy early, will be followed at least 30 days following cessation of study drug unless withdrawal of consent occurs.

There will be one scheduled visit 30 days following completion of the trial (after cycle 24 if not continuing on to the extension phase) or cessation of study drug. The following procedures will be performed at the follow-up visit:

- Medical history and Assessment for adverse events
- Concomitant medications
- PE with dermatologic examination (Photograph(s) of new or changing cutaneous lesions, lymphedema, or other)
- Height, weight, and vital signs: temperature, pulse, blood pressure, respiratory rate, oxygen saturation by pulse oximeter
- Performance Status: Karnofsky/Lansky Performance Score.
- Laboratory studies as outlined in section [6.1 Screening Assessments](#)
- Pregnancy testing for all subjects of childbearing potential: serum or urine pregnancy testing
- Collect unused study drug and diary
- If not done within 3 months of the study termination the following needs be to performed:
 - Ophthalmologic exam as outlined in section [6.1 Screening Assessments](#)
 - ECHO as outlined in [6.1 Screening Assessments](#)

6.5 Unscheduled Visits

Unscheduled visits will occur for any symptoms or concerns for toxicity, drug tolerance, acute changes in physical well-being, or other concerns. Study subjects will call study team representative and be seen in the clinic or by their local medical provider, or emergency department with communication with study team.

6.6 Subject Completion/Withdrawal

Criteria for withdrawal of subjects and plans for provision of care after withdrawal.

Subjects may withdraw from the study at any time without prejudice to their care. They may also discontinue study participation at the discretion of the Investigator for lack of adherence to study treatment or visit schedules, AEs, due investigator discretion, or family/subject preference. The Investigator or the Sponsor (if applicable) may also withdraw subjects who violate the study plan, or to protect the subject for reasons of safety or for administrative reasons. It will be documented whether or not each subject completes the clinical study. If the Investigator becomes aware of any serious, related adverse events after the subject completes or withdraws from the study, they will be recorded in the source documents and on the CRF.

7 SUPPORTIVE CARE AND CONCOMITANT MEDICATION

7.1 Other Treatment(s)

All subjects will be allowed to receive concomitant medication and/or other non-medication treatment (e.g., rescue surgery) when clinically indicated to control comorbidities and/or complications of their VA. Rescue surgery is defined as a salvage intervention, and includes e.g. debulking surgery, orthopedic surgery, invasive vascular surgeries/procedures. As much as possible, surgery targeting VA-related lesion volume reduction should be avoided. Systemic therapy targeting Ras/MAPK pathway other than trametinib and/or any investigational/not approved medication for VA are not allowed during the conduct of the study.

During the course of the study, the subject must also not receive anti angiogenic agents for the purpose to treat VA.

The subject must discontinue from specific treatment with small molecules (such as mTOR inhibitors, AKT inhibitors) before any of study related assessments and at least 30 days before study treatment start per inclusion/exclusion criteria.

Subjects are not allowed to receive any other investigational drugs.

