7.2 Concomitant Therapy

Subjects will be instructed to inform the investigator prior to starting any new medications from the time of first dose of study treatment until the end of the study.

At each study visit subjects should be asked: “Have you taken any new medicines, other than those provided in this study, since your last visit/contact?” or “Has your child needed to take any medicines, other than those provided in this study, since his/her last visit/contact?”.

All medications (other than trametinib) including non-prescription medication(s), vitamins and herbal product(s), taken during the study will be recorded in the CRF. Any significant non-drug therapies should also be noted in the subject’s CRF.

Subjects should receive all necessary supportive care during the study.

Examples of permissible concomitant therapies:

- Transfusions of blood and blood components
- Pain relief medication
- Anti-infective medications (see prohibited and cautioned medications in [Section 7.2.1 and 7.3](#)). Investigators should discuss prescription of anti- fungal, anti-viral agents with Novartis.
- Treatment for concomitant medical conditions, adverse events (see prohibited and cautioned medications in [Section 7.2.1 and 7.3](#))
- Supplemental nutrition (enteral, parenteral)
- Routine vaccinations including live vaccines as needed based on subject age
- Supportive care use of anticoagulants and compression garments is allowed. Subjects must have been using these interventions in an unchanged manner for 30 days before study enrollment
- Replacement therapy (e.g., thyroxine, insulin, or physiologic or stress doses of corticosteroid replacement therapy for adrenal or pituitary insufficiency, etc.) are permitted. Steroid premedication for imaging scans is allowed.

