8.2.1.2 Other Radiographic Assessment

Other imaging modalities including, but not limited to Computed tomography (CT) Scan, Ultrasound (US) or X-ray may be utilized for radiographic assessment criteria either in supplement to or in replacement of MR imaging as noted above. Target lesions should be selected on the basis of their size and their suitability for accurate repeated measurements (either by imaging techniques or clinically). The modality and imaging methods will be determined for enrollment screening and the same method of assessment, and the same technique, should be used to characterize each target lesion at screening and during each imaging follow up. Examples of imaging would be X-Ray for bone disease, ultrasound for pleural effusions, dexascan for lymphatic anomalies with bone lesions, and US (contrast or non-contrast for superficial lesions to assess size and other characteristics such as flow.

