8.3.2 Response Criteria for Overall Response

The primary endpoint of this VATCH sub-protocol is to determine whether the MEK inhibitor trametinib administered once a day on a continuous dosing schedule to subjects with Ras/MAPK pathway driven Vascular Anomalies provides an objective response at the end of cycle 6. Assessment of response is an individualized response criterion based on radiologic assessment, Patient Reported Outcome Measurements (composite score) and Clinical Benefit Assessment. Disease Response is determined by the local institution/investigator and is defined below.

Clinically meaningful response:

A clinically meaningful response includes a substantial response, Intermediate response or stable disease at the timing of protocol assessment.

Assessment of individualized response criteria after 6 cycles for primary endpoint and then every 6 months.

Substantial response:

- Improvement in Radiologic assessment (if applicable) by 20% AND
- Improvement in Global Health PROs by 3T-score points* AND
- Improvement in at least 1 CBA as reported by the clinician AND
- No clinically meaningful worsening in any measure

Intermediate response:

- Improvement in Radiologic assessment (if applicable) by 20% OR
- Improvement in Global Health PROs by 3 T-score points* OR
- Improvement in at least 1 CBA as reported by the clinicians AND
- No clinically meaningful worsening in any measure

Stable disease:

- No clinically meaningful improvement or worsening from screening in
 - Radiologic assessment (if applicable), OR
 - Global Health PROs*, OR
 - CBA as reported by the clinician

Worsening disease:

- Clinically meaningful worsening in
 - Radiologic assessment (if applicable) by 20%, OR
 - Global Health PROs by 3T-score points*, OR
 - CBA as reported by the clinician
 - **Regardless** of any concomitant improvement in other measures.

*Prior review articles have indicated that a change of 2 to 6 T-score points is the minimum important change (MIC) for PROMIS measures. PROMIS leadership recommends 3 T-score points as the MIC^{61,62}.

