8.3.3 Duration of Response

Duration of Overall Response: The overall response (substantial or intermediate) duration is measured from the time of primary endpoint measurement (6 cycles) until the first date that recurrent or progressive disease is objectively documented (taking as reference for progressive disease the smallest measurements recorded since the treatment started).

Duration of Stable Disease: Stable disease is measured from the start of the treatment until the worsening disease criteria are met, or patient on evaluation has a substantial or intermediate response.

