Grade 4 Impairment of urine output or respiratory distress

Grade 5 Death

Bone involvement of VA:

Grade 0	No bone involvement of VA
Grade 1	Asymptomatic, radiologic findings only
Grade 2	Symptomatic, but not interfering with ADL, medication/intervention may be needed
Grade 3	Altered ADL secondary to symptoms: pain, fracture
Grade 4	Complete loss of function

Effusions caused by VA (pleural, cardiac, ascites):

Grade 0	No effusions caused by VA (pleural, cardiac, ascites)
Grade 1	Asymptomatic, radiologic findings only
Grade 2	Symptomatic, but not requiring immediate intervention
Grade 3	Requiring intervention, fluid removal, tube drainage, fluid replacement
Grade 4	Requiring ventilation or more aggressive surgical support

Lymphedema caused by VA:

Grade 0	No lymphedema caused by VA
Grade 1	Intermittent swelling, when swelling skin will “pit”, Relief and reduction with elevation
Grade 2	Tissue is firmer, less pitting, no relief with elevation
Grade 3	Hard (fibrotic) skin, thickening of surface, Increase in circumference
Grade 4	All of the above with skin breakdown with or without infection

AVM Skin Involvement:

Grade 0	No skin discoloration or stain
Grade 1	Skin discoloration or stain, warmth, shunting on Doppler
Grade 2	Enlargement, pulsation-thrill, bruit with or without minor ulceration or pain

Grade 3	Moderate ulceration, bleeding, or pain
Grade 4	Severe ulceration, bleeding, pain, or other significant morbidity

Physical Disability:

Grade 0	No disability
Grade 1	Mildly impaired, Performs ADLs
Grade 2	Moderately impaired, Needs help with some ADLs
Grade 3	Severely impaired, needs help with all ADLs
Grade 4	Unable to perform any intentional physical activity

Protein Losing Enteropathy (PLE)

Grade 0	No PLE
Grade 1	Mildly abnormalities in lab work (Albumin, TP, Alpha -1 anti-trypsin etc.)
Grade 2	Moderate abnormalities in lab work, no replacement needed, may need low-fat diet
Grade 3	Significant impairment in lab work, need for replacement, strict low-fat diet, MRL intervention
Grade 4	Hospitalization, Requiring replacement and intervention (MRL with treatment, surgical procedures)

Hypoglycemia

Grade 0	No hypoglycemia
Grade 1	Mildly impaired, Episodes but limited intervention
Grade 2	Moderately impaired, Need for frequent interventions
Grade 3	Severely impaired, need for frequent glucose monitoring and IV replacement
Grade 4	Hypoglycemic events requiring hospitalization

Seizures

Grade 0	No need for antiepileptic medication

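### A target lesion or followed effusion made smaller by a permitted procedure can be scored as a trametinib response, because 8.3.2 and 8.3.3 contain no rule for procedures

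*Protocol*

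**What the plan says.** **Procedures on study.** Protocol 7.1 opens with "All subjects will be allowed to receive concomitant medication and/or other non-medication treatment (e.g., rescue surgery) when clinically indicated", for comorbidities or complications of the vascular anomaly. It describes rescue surgery as a salvage intervention that "includes e.g. debulking surgery, orthopedic surgery, invasive vascular surgeries/procedures". The only limit on surgery that shrinks a lesion is "As much as possible, surgery targeting VA-related lesion volume reduction should be avoided". Section 7.2 adds "Any significant non-drug therapies should also be noted in the subject’s CRF" and draws no link to response.

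**Response scoring.** Under 8.3.2 the local investigator classifies each subject at the end of cycle 6 against screening. An intermediate response needs one improvement, the first listed being "Improvement in Radiologic assessment (if applicable) by 20% OR". The alternatives are a 3-point Global Health gain or improvement in one clinical benefit assessment (CBA). The one bar is clinically meaningful worsening in any measure, and a procedure is not listed as worsening.

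**Effusions.** Section 8.2.1.2 names "ultrasound for pleural effusions" as an example of imaging. Appendix X has an effusion scale whose Grade 3 reads "Requiring intervention, fluid removal, tube drainage, fluid replacement", and it tells the assessor to look back over 7 days.

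**Duration.** In 8.3.3 a response runs "until the first date that recurrent or progressive disease is objectively documented".

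Sections 8.3.1, 9.3 and 10.4.1 also say nothing about a lesion treated by a procedure.

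**The concern.** The trial has no control arm, so nothing absorbs the effect of procedures on the response rate. The endpoint is meant to measure trametinib; as defined, it measures trametinib plus any procedure performed before the cycle-6 visit. Subjects who do badly are the more likely to need salvage, so a rule that can credit the salvage to the drug tends to favour the drug.

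The protocol guards against this at entry. Section 5.2 excludes debulking or other major surgery within 30 days, and sclerotherapy or embolization within 14 days, before consent. No matching scoring rule covers the 24 weeks over which the endpoint is measured. Procedures in that period are foreseeable: 1.1 lists interventional procedures for lymphatic flow among supportive measures, and 11.5 lists lymphatic interventions, surgery and vascular occlusive procedures as current therapy.

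The same scoring feeds the futility look after 16 subjects, the final decision on 39, and the duration of response.

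**Working it through.** **Applying the text to two cases**

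1. *A target lesion is debulked or embolized in cycle 4.* Section 7.1 permits it as rescue. If the lesion measures at least 20% smaller than at screening at the end of cycle 6 and no measure has worsened, 8.3.2 gives at least an intermediate response. The duration clock in 8.3.3 then starts.
2. *A pleural effusion is followed by ultrasound and by the effusion CBA, and is drained two weeks before the visit.* The ultrasound measure can improve. The drainage lies outside the 7-day CBA window, so the grade can fall below 3 as well. Two components can improve through one procedure.

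**Do other clauses close the gap?**

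- Abstract and Experimental Design Schema: signs of worsening should lead to an earlier response assessment. This is a recommendation, and neither place says that an early worsening fixes the cycle-6 result.
- Experimental Design Schema: therapy is discontinued on evidence of worsening disease. But 10.4.1(b) leaves removal for worsening to the investigator, and 4.6 leaves it to the physician's decision.
- 10.4.1: rescue surgery is not itself a reason for removal.
- 8.3.2: worsening overrides improvement elsewhere. This acts only on what is measured at the assessment.

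**Size, as an illustration**

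Inputs from 9.1: null rate 0.40, alternative 0.65, n1 = 16 (stop at 6 or fewer), n = 39 (promising at 20 or more). One input is assumed: q, the share of true non-responders converted to scored responders by a procedure.

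The apparent rate is p = 0.40 + 0.60q. Let r1 be the stage-1 stopping limit and c the final cut. Then

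P(promising) = sum over x from r1+1 to 16 of b(x; 16, p) × P(Bin(23, p) ≥ c − x).

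The plan's own figures come first. With r1 = 6 and c = 20, power at 0.65 is 0.9575, in line with the stated 90% or more. The type I error at 0.40 is 0.0926, not the stated 0.05 or less. That mismatch is a separate error and has nothing to do with procedures. To keep the two apart, the table also uses the Simon optimal boundaries for these inputs: stop at 7 or fewer of 16, promising at 21 or more of 39 (type I error 0.0460, power 0.9012).

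| q | p | Extra responders in 39 (39 × 0.60 × q) | P(promising), boundaries that hold alpha | P(promising), boundaries as written |
|---|---|---|---|---|
| 0 | 0.40 | 0 | 0.046 | 0.093 |
| 5% | 0.43 | 1.2 | 0.095 | 0.172 |
| 10% | 0.46 | 2.3 | 0.173 | 0.283 |
| 15% | 0.49 | 3.5 | 0.281 | 0.419 |

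One or two converted subjects in 39 are enough to matter.

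**The case against.** A reader might infer that every lesion shrunk by a procedure is scored as a response and that the error can run only one way. The documents do not support that. A subject deteriorating enough to need salvage should normally be assessed at that point and may be classed as worsening and removed. Several Appendix X scales grade the need for intervention or hospitalization as 3 or 4, so a procedure inside the 7-day window can raise the CBA grade. Recovery from surgery can lower the Global Health score. Either can block a response. What remains is the subject whose early assessment was missed or did not meet worsening, who was kept on therapy, and whose procedure fell well before the visit.

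Three further points stand in part:

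- **Drainage is permitted by inference.** Section 7.1 does not name it; it falls under other non-medication treatment. The Appendix X wording describes severity and is not permission.
- **Stable disease changes the mechanism.** The synopsis and 8.3.2 count stable disease towards response, whereas 8.3.3 treats overall response as substantial or intermediate only. Where stable counts, non-responders are essentially the worsened subjects. A procedure must then bring every measure out of the worsening range, which may make conversion rarer than a single improvement would suggest.
- **The analysis plan is not shown.** Handling of rescue is often left to it. Here, however, the response definition is written out in the protocol and applied by local investigators, so a later analysis rule would have to override 8.3.2.

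It would also be wrong to attribute the whole of the as-written column to procedures, since its 9.3% starting value comes from the boundaries.

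**Conclusion.** The point holds in a limited form. As 7.1, 8.3.2 and 8.3.3 read, a target lesion or followed effusion reduced by a procedure can be recorded as a trametinib response (or as stable disease, where that counts) when no measure meets worsening at the visit. The early-assessment and removal clauses narrow the gap without closing it.

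How often this would happen cannot be known from the documents. The rise from 4.6% to 9.5%, 17.3% and 28.1% at q = 5%, 10% and 15% rests on an assumed q, a true rate at the 40% null, and boundaries that hold alpha. It shows how sensitive a 39-subject single-arm trial is to a few misattributed responses; it is not a forecast.

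This should be fixed, and settled before the 16-subject interim, which uses the same scoring.

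**What to change.** Three wording changes, all to scoring and recording:

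1. **8.3.2.** State that a subject who has a lesion-directed procedure on a target lesion or a followed CBA domain between baseline and the cycle-6 assessment counts as a non-responder for the primary endpoint. List which procedures qualify (for example debulking, embolization, sclerotherapy, drainage of a followed effusion). Report the count that ignores procedures as a sensitivity analysis.
2. **8.3.3.** End the duration of response at the date of such a procedure.
3. **7.2.** Have the CRF entry for non-drug therapies record the date and anatomical site, so that the procedure can be matched to the followed lesion or domain. At present only significant non-drug therapies are to be noted, and the scripted visit question asks only about medicines.

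Care under 7.1 is unchanged. The cost is an amendment and a small CRF addition. The downside is that an occasional true responder with a procedure on a followed site is counted as a non-responder, so the reported rate may be somewhat lower; the sensitivity count shows by how much. Treating the affected lesion as not evaluable is a possible alternative. Whichever rule is chosen should be written down before the interim.
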